7.6. Treatment Compliance

The investigator or designee will assess compliance of the patient at each visit, based on a review of the patient's CareLink reports, glycemic control, adherence to the visit and treatment schedule, and completion of the patient's study diary. Patients who are deemed noncompliant will receive additional diabetes education and training, as required, and the importance of compliance with the protocol will be reinforced. Patients who, in the opinion of the investigator, are deemed consistently noncompliant may be discontinued from the study. No specific study data will be collected to analyze treatment compliance.

7.7. Concomitant Therapy

The following concomitant medications

- are NOT allowed at any time during the study;
 - Afrezza® (inhaled insulin)
 - Any noninsulin diabetes treatment therapy
 - Acetaminophen
 - Systemic glucocorticosteroid
 - IV, IM, SC, oral
 - except in the case of replacement therapy for adrenal insufficiency
- ARE allowed for a maximum of 48 hours during each treatment period
 - Basal insulin

- Regular human insulin or a nonstudy rapid-acting analog insulin
- ARE allowed at any time
 - Topical, inhaled, intraocular, intra-articular, or intranasal steroid preparations

7.8. Treatment after the End of the Study

7.8.1. Treatment after Study Completion

LY900014 will not be made available to patients after conclusion of the study. Rapid-acting insulin analogs are available in all countries for use as prandial/pump insulin.

7.8.2. Special Treatment Considerations

After discontinuation of IP at the end of the treatment period or earlier, randomized patients should start a nonstudy rapid-acting analog insulin via CSII.

Investigators should provide patients with appropriate guidance for glucose monitoring and insulin dose adjustment throughout the follow-up period to maintain glycemic control.

8. Discontinuation Criteria

8.1. Discontinuation from Study Treatment

Patients who need to discontinue from study treatment will also be discontinued from the Study. Please refer to Section 8.2.

8.1.1. *Discontinuation of Inadvertently Enrolled Patients*

If the sponsor or investigator identifies a patient who did not meet enrollment criteria and was inadvertently enrolled, then the patient should be discontinued from study. If the investigator and the sponsor CRP/CRS agree that it is medically appropriate to continue, the investigator must obtain documented approval from the sponsor CRP/CRS to allow the inadvertently enrolled patient to continue in the study with IP. Safety follow-up is as outlined in Section 2 (Schedule of Activities), Section 9.2 (Adverse Events), and Section 9.4 (Safety) of the protocol.

8.2. Discontinuation from the Study

Patients will be discontinued in the following circumstances:

- The investigator may decide that the patient should stop IP. If this decision is made because of an AE, SAE, or a clinically significant laboratory value, the study drug is discontinued for that patient and appropriate measures are to be taken. Lilly or its designee is to be alerted immediately
- The patient may decide to stop IP
- The patient becomes pregnant
- If an investigator, study site personnel performing assessments, or patient is unblinded, the patient must discontinue IP
- Frequent use of prohibited concomitant medication
- Use of pump other than the Medtronic MiniMed 670G.
- The patient has not used IP for more than 3 consecutive days
- Enrollment in any other clinical study involving an IP or enrollment in any other type of medical research judged not to be scientifically or medically compatible with this study
- Participation in the study needs to be stopped for medical, safety, regulatory, or other reasons consistent with applicable laws, regulations, and good clinical practice
- A patient experiences any episode of clinically diagnosed Diabetic Ketoacidosis (DKA) during the study
 - DKA is defined as an acute metabolic complication of diabetes characterized by hyperglycemia, hyperketonemia, and metabolic acidosis. Hyperglycemia causes an osmotic diuresis with significant fluid and electrolyte loss. DKA causes nausea, vomiting, and abdominal pain and can progress to cerebral

edema, coma, and death. DKA is diagnosed by detection of hyperketonemia and anion gap metabolic acidosis in the presence of hyperglycemia.

Treatment involves volume expansion, insulin replacement, and prevention of hypokalemia

- A patient participating in the pilot experiences any episode of severe hypoglycemia during the first 3 days of the pilot safety assessment
- A patient experiences >1 episode of severe hypoglycemia during the study
- A pilot patient's designated study companion does not comply with assigned responsibilities or is no longer available during pilot and transfer of study companion responsibilities is not possible for remainder of pilot safety assessment
- Investigator decision
 - the investigator decides that the patient should be discontinued from the study
 - if the patient, for any reason, requires treatment with another therapeutic agent that has been demonstrated to be effective for treatment of the study indication, discontinuation from the study occurs prior to introduction of the new agent
- Subject decision
 - the patient requests to be withdrawn from the study
- **Discontinuation due to a hepatic event or liver test abnormality:** patients who are discontinued due to a hepatic event or liver test abnormality should have additional hepatic safety data collected via electronic case report form (eCRF).
- Discontinuation for abnormal liver tests **should be** considered by the investigator when a patient meets one of the following conditions after consultation with the Lilly-designated medical monitor:
 - ALT or AST >8X ULN
 - ALT or AST >5X ULN for more than 2 weeks
 - ALT or AST >3X ULN and TBL >2X ULN or international normalized ratio >1.5
 - ALT or AST >3X ULN with the appearance of fatigue, nausea, vomiting, right upper-quadrant pain or tenderness, fever, rash, and/or eosinophilia (>5%)
 - alkaline phosphatase (ALP) >3X ULN
 - ALP >2.5X ULN and TBL >2X ULN
 - ALP >2.5X ULN with the appearance of fatigue, nausea, vomiting, right quadrant pain or tenderness, fever, rash, and/or eosinophilia (>5%)

Patients discontinuing from the study prematurely for any reason should complete AE and other safety follow-up per Section 2 (Schedule of Activities), Section 9.2 (Adverse Events), and Section 9.4 (Safety) of this protocol, with the exception of those who discontinue during the lead-in period will not need to have laboratory tests drawn.

8.3. Lost to Follow-up

A patient will be considered lost to follow-up if he or she repeatedly fails to return for scheduled visits and is unable to be contacted by the study site. Site personnel are expected to make diligent attempts to contact patients who fail to return for a scheduled visit or were otherwise unable to be followed up by the site. Due diligence efforts should be documented in eCRF.

Lilly personnel will not be involved in any attempts to collect vital status information.

9. Study Assessments and Procedures

Section 2 lists the Schedule of Activities, with the study procedures and their timing (including tolerance limits for timing).

Appendix 2 lists the laboratory tests that will be performed for this study.

Unless otherwise stated in the subsections below, all samples collected for specified laboratory tests will be destroyed within 60 days of receipt of confirmed test results. Certain samples may be retained for a longer period, if necessary, to comply with applicable laws, regulations, or laboratory certification standards.

9.1. Efficacy Assessments

9.1.1. Primary Assessments

Percentage of time in range (%) of target SG values collected.

9.1.2. Secondary Assessments

- Percentage of time in range (%) of hypoglycemic SG values collected
- Percentage of time (%) per week spent in Auto Mode
- Mean SG value
- Rate and incidence of hypoglycemia events
- Mean total daily basal insulin dose
- Mean total daily bolus insulin dose

9.1.3. Appropriateness of Assessments

All assessments included in this study are generally regarded as reliable and accurate with respect to diabetes.

9.1.4. Study Procedures

9.1.4.1. Continuous Glucose Monitoring

The Medtronic MiniMed 670G System consists of the following devices:

- MiniMed 670G Insulin Pump,
- Guardian Link (3) Transmitter,
- Guardian Sensor (3),
- CONTOUR NEXT Link 2.4 Glucose Meter.

Patients will use all of the System components throughout the trial. All therapy adjustments should be based on measurements obtained using the CONTOUR NEXT Link 2.4 Glucose Meter and not on values provided by the Guardian Sensor (3). The Guardian Sensor (3) is intended for use with the Medtronic MiniMed 670G system to continuously monitor glucose levels in patients with diabetes. It is intended to provide an indication of when a finger stick may be required, for detecting trends and tracking patterns, and to be used by the Medtronic MiniMed 670G system to

automatically adjust basal insulin levels. The Guardian Sensor (3) is indicated for 7 days of continuous use. The sensor must be calibrated at a minimum of every 12 hours, but it is recommended that the sensor is calibrated 3 or 4 times each day.

Patients must use SMBG values taken only from finger-sticks for calibrations. Do not use alternative BG site testing (forearm, palm, etc.) for sensor calibration.

Avoid products-containing acetaminophen while using the Medtronic MiniMed 670G system. Taking medications with acetaminophen, including, but not limited to Tylenol®, fever reducers, or cold medicine, while wearing the sensor may falsely raise SG readings.

9.1.4.3. Infusion Set Changes

Patients should change their infusion set and reservoir every 3 days.

The patient's study diary will be used to collect unplanned infusion set changes, including date and time of change and the primary reason for unplanned change.

- Pump occlusion alarm,
- Unexplained high BG,
- Infusion site reaction (pain, redness or swelling at infusion site), or
- Infusion set problem (infusion set kinked, pulled out, leaking, reservoir empty, etc.).

Unexplained hyperglycemia is defined as high BG >300 mg/dL that cannot be explained by a missed prior bolus, dietary indiscretion, rebound or treatment of hypoglycemia, a pump failure, an empty pump reservoir, an infusion set complication (for example, kinked, came out, leaking), or an infusion site complication (for example, pain, redness).

Investigators will review pump occlusion alarms, unexplained hyperglycemia, and unplanned infusion set changes with patients at each visit.

Any interruption of CSII will need to be documented in the eCRF. When patients resume use of pump following the interruption, the infusion set change should not be entered as an unplanned infusion set change in the study diary.

9.1.4.4. Diabetes Training

Training will include the following:

- Verify Contour Next LINK meter is paired and communicating with pump
- Frequency of reservoir and infusion set changes
- Frequency of sensor changes
- Infusion site and sensor site rotation
- Responding to pump and sensor alerts and alarms
- Unexplained hyperglycemia management
- Patient's ability to carb count
- Patient's ability use the pump's bolus calculator to determine bolus and correction doses
- Patient's ability to use bolus types appropriately
- Patient's ability to treat hypoglycemia

Appropriate site personnel will administer training and education using locally approved diabetes education/training materials and programs or by using other materials that may be provided by the sponsor. Patients may be provided additional training and education at visits following Visit 2, based upon patient needs.

9.2. Adverse Events

Investigators are responsible for monitoring the safety of patients who have entered this study and for alerting Lilly or its designee of any event that seems unusual, even if this event may be considered an unanticipated benefit to the patient.

The investigator is responsible for the appropriate medical care of patients during the study.

Investigators must document their review of each laboratory safety report.

The investigator remains responsible for following, through an appropriate health care option, AEs that are serious or otherwise medically important, considered related to the IP, the medical device or the study procedures that caused the patient to discontinue the IP before completing the study. The patient should be followed up until the event resolves, stabilizes with appropriate diagnostic evaluation, or is reasonably explained. The frequency of follow-up evaluations of the AE is left to the discretion of the investigator.

Lack of drug effect is not an AE in clinical studies, because the purpose of the clinical study is to establish treatment effect.

After the informed consent form (ICF) is signed, study site personnel will record via electronic data entry the occurrence and nature of each patient's preexisting conditions, including clinically significant signs and symptoms of the disease under treatment in the study. In addition, site personnel will record any change in the condition(s) and any new conditions as AEs.

Investigators should record their assessment of the potential relatedness of each AE to protocol procedure, IP, via electronic data entry.

The investigator will interpret and document whether or not an AE has a reasonable possibility of being related to study treatment, study device, or a study procedure, taking into account the disease, concomitant treatment, or pathologies.

A “reasonable possibility” means that there is a cause and effect relationship between the IP, medical device, and/or study procedure and the AE.

The investigator answers yes/no when making this assessment.

Planned surgeries and nonsurgical interventions should not be reported as AEs unless the underlying medical condition has worsened during the course of the study.

If a patient’s IP is discontinued as a result of an AE, study site personnel must report this to Lilly or its designee via electronic data entry, clarifying, if possible, the circumstances leading to any dosage modifications, or discontinuations of treatment.

9.2.1. Serious Adverse Events

An SAE is any AE from this study that results in one of the following outcomes:

- death
- initial or prolonged inpatient hospitalization
- a life-threatening experience (that is, immediate risk of dying)
- persistent or significant disability/incapacity
- congenital anomaly/birth defect
- important medical events that may not be immediately life-threatening or result in death or hospitalization but may jeopardize the patient or may require intervention to prevent one of the other outcomes listed in the definition above. Examples of such medical events include allergic bronchospasm requiring intensive treatment in an emergency department or at home, blood dyscrasias or convulsions that do not result in inpatient hospitalization, or the development of drug dependency or drug abuse.
- Severe hypoglycemic events: episodes of severe hypoglycemia as determined by the investigator according to the definition provided in Section 9.4.2 must be reported as SAEs

All AEs occurring after signing the ICF are recorded in the case report form (CRF) and assessed for serious criteria. The SAE reporting to the sponsor begins after the patient has signed the ICF and has received IP. However, if an SAE occurs after signing the ICF, but prior to receiving IP, the SAE should be reported to the sponsor according to SAE-reporting requirements and timelines (see Section 9.2) if it is considered reasonably possibly related to study procedure.

Study site personnel must alert Lilly or its designee of any SAE within 24 hours of investigator awareness of the event via a sponsor-approved method. If alerts are issued via telephone, they are to be immediately followed with official notification on study-specific SAE forms. This 24-hour notification requirement refers to the initial SAE information and all follow-up SAE information. Patients with a serious hepatic AE should have additional data collected using the eCRF.

Pregnancy (during maternal exposure to IP) does not meet the definition of an AE. However, to fulfill regulatory requirements any pregnancy should be reported following the SAE process to collect data on the outcome for both mother and fetus.

Investigators are not obligated to actively seek AEs or SAEs in subjects once they have discontinued and/or completed the study (the patient disposition CRF has been completed). However, if the investigator learns of any SAE, including a death, at any time after a subject has been discharged from the study, and he or she considers the event reasonably possibly related to the study treatment or study participation, the investigator must promptly notify Lilly.

9.2.1.1. Suspected Unexpected Serious Adverse Reactions

Suspected unexpected serious adverse reactions (SUSARs) are serious events that are not listed in the IB and that the investigator identifies as related to IP or procedure. United States 21 CFR 312.32 and European Union Clinical Trial Directive 2001/20/EC and the associated detailed guidance or national regulatory requirements in participating countries require the reporting of SUSARs. Lilly has procedures that will be followed for the identification, recording and expedited reporting of SUSARs that are consistent with global regulations and the associated detailed guidance.

9.2.2. Complaint Handling

Lilly collects product complaints on IP, materials provided, and drug delivery systems used in clinical studies to ensure the safety of study participants, monitor quality, and facilitate process and product improvements.

Patients will be instructed to contact the investigator as soon as possible if he or she has a complaint or problem with the IP or their insulin pump so that the situation can be assessed.

Any insulin pump issue will be assessed at the investigative site and if not resolved the investigator should report the complaint directly to the pump manufacturer in accordance with the product labeling. Investigators should report these complaints as they would for products in the marketplace.

- Complaints on IP must be reported to Lilly by site staff within 24 hours of notification, or within 24 hours of study/site personnel becoming aware of a product issue, regardless of the availability of the complaint sample.
- Investigative sites must retain the IP under appropriate storage conditions, if available or when obtained, until instructed to return it to Lilly.

- Product complaints for Non-Lilly Products (including concomitant drugs and insulin pumps) that do not have a Lilly Product Batch or Control number are reported directly to the manufacturer per product label.
- Follow the instructions outlined in the Product Complaint Form for other reporting instructions.

9.3. Treatment of Overdose

Excess insulin administration may result in hypoglycemia. Refer to the IB for LY900014 and product label for Humalog.

9.4. Safety

9.4.1. Hypoglycemia

Patients are encouraged to perform SMBG whenever hypoglycemia may be suspected, either by symptoms experienced, CGM reading or perceived increased risk as related to dietary intake, physical activity, inadvertent or atypical insulin dosing or when prompted by pump alerts. All patients will be instructed to consider a BG ≤ 70 mg/dL to be hypoglycemia and treat appropriately.

If a hypoglycemic event is suspected, the patient should record the BG value, any associated symptoms, and the treatment administered in the study diary. The patient should contact the site as necessary. All hypoglycemia events (severe and nonsevere) must be reported on the hypoglycemia eCRF. All episodes of severe hypoglycemia must be reported as SAEs on the AE eCRF page and on the SAE eCRF page. Episodes of hypoglycemia not meeting the criteria for severe hypoglycemia should not be reported as an AE.

Hypoglycemia will be described using the following definitions:

- **Documented Glucose Alert (Level 1); BG ≤ 70 mg/dL:**
 - **Documented symptomatic hypoglycemia:** an event with typical symptoms of hypoglycemia.
 - **Documented asymptomatic hypoglycemia:** an event without typical symptoms of hypoglycemia.
 - **Documented unspecified hypoglycemia:** with no information about symptoms of hypoglycemia available (this has also been called unclassifiable hypoglycemia).
- **Documented Clinically Significant Hypoglycemia (Level 2) with similar criterion as above except for threshold BG < 54 mg/dL**
 - **Documented symptomatic hypoglycemia**
 - **Documented asymptomatic hypoglycemia**
 - **Documented unspecified hypoglycemia**
- **Severe Hypoglycemia (Level 3):** during these episodes, patients have an altered mental status and cannot assist in their own care, may be semiconscious or unconscious, or experience coma with or without seizures, and the event requiring assistance of another person to actively administer carbohydrate, glucagon, or other resuscitative actions. Blood glucose measurements may not be available during such an event, but neurological

recovery attributable to the restoration of BG concentration to normal is considered sufficient evidence that the event was induced by a low BG concentration (BG \leq 70 mg/dL [3.9 mmol/L]).

- **Other Hypoglycemia**
 - **Nocturnal Hypoglycemia:** any documented hypoglycemic event (including severe hypoglycemia) that occurs between bedtime and waking.
 - **Probable Symptomatic Hypoglycemia:** an event during which symptoms are present, but BG measurement was not reported.
 - **Overall (or Total) Hypoglycemia:** this category combines all cases of hypoglycemia (documented hypoglycemia and probable symptomatic hypoglycemia, including severe hypoglycemia). Nocturnal and severe hypoglycemia are special cases of documented or probable hypoglycemia. If an event of hypoglycemia falls into multiple subcategories, the event is only counted once in this category.

Additional analysis of hypoglycemia events will be conducted using CGM data alone for threshold BG $<$ 50 mg/dL and $<$ 70 mg/dL.

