Appendix 1. Abbreviations and Definitions

Term	Definition
AE	adverse event: Any untoward medical occurrence in a patient or clinical investigation patient administered a pharmaceutical product that does not necessarily have a causal relationship with this treatment. An AE can therefore be any unfavorable and unintended sign (including an abnormal laboratory finding), symptom, or disease temporally associated with the use of a medicinal (investigational) product, whether or not related to the medicinal (investigational) product.
AIT	active insulin time
ALP	alkaline phosphatase
ALT	alanine aminotransferase
AST	aspartate aminotransferase
BG	blood glucose
blinding	
A single-blind study is one in which the investigator and/or his staff are aware of the treatment but the patient is not, or vice versa, or when the sponsor is aware of the treatment but the investigator and/his staff and the patient are not.
 
A double-blind study is one in which neither the patient nor any of the investigator or sponsor staff who are involved in the treatment or clinical evaluation of the patients are aware of the treatment received.

CGM	continuous glucose monitoring
CI	confidence interval
confirmed pump occlusion	An interruption in continuous pump insulin flow that triggered an occlusion alarm that would not clear, after confirming that the pump and infusion set are in place without leaks or kinks in the system.
CR	carb ratio
CRF	case report form
CRP/CRS	clinical research physician: Individual responsible for the medical conduct of the study. Responsibilities of the CRP may be performed by a physician, clinical research scientist, global safety physician, or other medical officer.
CSII	continuous subcutaneous insulin infusion
CSR	clinical study report
DKA	diabetic ketoacidosis
ECG	electrocardiogram

eCRF	electronic case report form
enroll	The act of assigning a patient to a treatment. Patients who are enrolled in the trial are those who have been assigned to a treatment.
enter	Patients entered into a trial are those who sign the informed consent form directly or through their legally acceptable representatives.
ERB	ethical review board
GCP	good clinical practice
HbA1c	hemoglobin A1c
IB	Investigator's Brochure
ICF	informed consent form
ICH	International Council for Harmonisation

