6.10.2. Adverse Events

Events that are newly reported after the first dose of rapid-acting insulin provided as study drug (ie, open-label Humalog used during the lead-in period or IP used during each of the two 4-week randomized treatment periods) or are reported to worsen in severity from baseline (defined in [Table ITSM.6.2](#) for each specific study period) will be considered treatment-emergent adverse events (TEAEs). Events that continue during more than 1 study period (lead-in, Period I, Period II) with the same severity will only be counted once for the first study period.

The MedDRA Lowest Level Term (LLT) will be used in the treatment-emergent assessment. The maximum severity for each LLT during the baseline period will be used as baseline severity. For events occurring on the day of first dose of blinded insulin provided in this study during each treatment period (lead-in, Period I and Period II), the CRF-collected flag will be used to determine whether the event started or worsened post-treatment, and/or the treatment of which period the AE should be assigned.

In an overview table, the number and percentage of patients who experienced a TEAE, experienced a serious adverse event (SAE), died due to an AE, and discontinued from study due to an AE will be summarized.

The number and percentage of patients with SAEs and who discontinued from the study due to an AE will be summarized using MedDRA PT nested within SOC if any such events occurred. Prescott's exact test will be performed for treatment comparison. The number and percentage of patients with TEAEs will be summarized by treatment using MedDRA PT nested within SOC. Events will be ordered by decreasing frequency within SOC. As an additional table, the percentages of patients with TEAEs will be summarized by treatment using MedDRA PT (without regard to SOC). Events will be ordered by decreasing frequency in total group. Statistical comparisons will be applied at both the SOC and PT levels. Prescott's exact test will be performed for treatment comparison.

The number and percentage of patients with TEAEs by maximum severity will be summarized by treatment using MedDRA PT nested within SOC. For each patient and TEAE on each treatment, the maximum severity for the MedDRA PT is the maximum postbaseline severity

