6.10.4.1. Hypoglycemic Events

Hypoglycemia events that occur during the study will be captured using a paper diary starting from Visit 2 through Visit 801. Whenever hypoglycemia is suspected, the patient should record the blood glucose value, any associated symptoms, and the treatment administered. A set of events is counted as 1 event in analysis if the duration between adjacent events is ≤ 30 minutes. The event with the highest severity will be selected for analysis. Severity will be determined in the order of: 1) whether it is a severe hypoglycemia, 2) whether it has symptoms of hypoglycemia reported, and 3) the lowest blood glucose value that occurred. If there are multiple events tied in all 3 aspects, the event with the largest number of nonmissing responses to the questions of nocturnal hypoglycemia and postmeal time frame will be selected. If there are still multiple events tied, the latest event (based on event time) will be selected.

The following types of hypoglycemia events will be derived in the analysis data sets: documented hypoglycemia, severe hypoglycemia, nocturnal hypoglycemia, probable symptomatic hypoglycemia, and overall hypoglycemia. Only severe hypoglycemia will be collected as AEs and all episodes of severe hypoglycemia will be considered as SAEs. Documented hypoglycemia (including documented symptomatic hypoglycemia, documented asymptomatic hypoglycemia, and documented unspecified hypoglycemia) will be based on $BG \leq 70$ mg/dL and $BG < 54$ mg/dL.

[Table ITSM.6.4](#) provides detailed statistical methods for each endpoint related to hypoglycemia. For these analyses, hypoglycemia events from first dose to last dose of IP will be summarized. Additional analyses for other types of hypoglycemic events not mentioned in the table may be conducted as needed.

A listing of patients with at least 1 severe hypoglycemia reported (as SAE) after randomization (including Visit 801) will be provided.

A list of MedDRA PTs will be used for the narrow search of potential severe hypoglycemia in spontaneously reported AEs. The events identified through the search strategy that are also reported as SAEs will be summarized and compared between treatments. Prescott's exact test will be used to assess the treatment difference in the proportion of patients with potential severe hypoglycemia.

Table ITSM.6.4. Summary of Analyses for Endpoints Related to Hypoglycemia

Endpoint	Analysis Period^a	Statistical Method

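### Protocol 9.4.1 and SAP 6.10.4.1 keep all nonsevere hypoglycemia out of AE reporting without exception, which conflicts with the AE and SAE definitions, and neither document says which rule prevails

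*Protocol*

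**What the plan says.** Protocol 9.4.1 sends every low to a dedicated form: "All hypoglycemia events (severe and nonsevere) must be reported on the hypoglycemia eCRF". Severe (Level 3) episodes also go on the AE and SAE pages. For all others the instruction is "Episodes of hypoglycemia not meeting the criteria for severe hypoglycemia should not be reported as an AE". SAP 6.10.4.1 takes the same line: "Only severe hypoglycemia will be collected as AEs and all episodes of severe hypoglycemia will be considered as SAEs".

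The general safety rules are wider. Protocol 9.2.1 opens with "An SAE is any AE from this study that results in one of the following outcomes", and the outcomes that follow include "initial or prolonged inpatient hospitalization". It also states that "All AEs occurring after signing the ICF are recorded in the case report form (CRF) and assessed for serious criteria". Appendix 1 defines an AE as "Any untoward medical occurrence in a patient or clinical investigation patient administered a pharmaceutical product", with no need for a causal link. None of these carves out hypoglycemia.

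On analysis, SAP 6.10.2 says that patients with SAEs and those "who discontinued from the study due to an AE will be summarized using MedDRA PT nested within SOC", with treatments compared by Prescott's exact test.

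**The concern.** Keeping routine lows off the AE page is a sensible way to avoid flooding the AE tables. The difficulty lies at the edge of the rule. An SAE must first be an AE, so an event that a site is told not to report as an AE never reaches the seriousness assessment. Likewise, a withdrawal can be counted as due to an AE only if an AE is on record as the reason.

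Hypoglycemia is a central safety question here. Protocol 5.1 describes the pilot as a test of whether the pump's control algorithm can safely be run with LY900014. At stake are expedited reporting of a serious low that falls short of Level 3, and the completeness of the SAE and AE-discontinuation comparisons between the two insulins. Sites could also handle the same event differently, each with a passage to support it.

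**Working it through.** The protocol and SAP give no figure to reproduce on this point, so the check is mainly a comparison of passages.

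1. **Does severe status already cover hospitalized lows?** Level 3 in Protocol 9.4.1 requires altered mental status, inability to look after oneself, and active help from another person. Protocol 9.4.2 leaves the decision to the investigator, based on medical need for help. Admission to hospital is not a criterion in either section, so a conscious patient admitted for a low can be nonsevere.

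2. **What does each rule give?**

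| Case | Following Protocol 9.4.1 and SAP 6.10.4.1 | Following Protocol 9.2.1 and Appendix 1 |
|---|---|---|
| Conscious patient hospitalized for the low alone | Hypoglycemia eCRF only; no AE, so no SAE | AE meeting the hospitalization criterion, so an SAE |
| IP stopped because of repeated nonsevere lows | No AE as reason; recorded under, for example, investigator or patient decision | Discontinuation due to an AE |

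The two columns disagree in both rows, and no passage says which governs.

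3. **What depends on the classification?**
   - Notification of the sponsor within 24 hours (Protocol 9.2.1).
   - The immediate alert when the investigator stops IP for an AE, SAE or significant laboratory value (Protocol 8.2).
   - The required report when IP ends because of an AE (Protocol 9.2).
   - The SAE and AE-discontinuation tables (Protocol 10.3.4, SAP 6.10.2).
   - The patient narratives (SAP 6.10.8).

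4. **Does the hypoglycemia eCRF stand in for this?** Not for timing. The Schedule of Activities transfers diary hypoglycemia to the eCRF at Visits 2, 4, 7, 10, 801 and early termination, plus Visit 5 for pilot patients. Visits 4 and 7 are at Weeks 0 and 4, so entry could come up to 4 weeks after an event, against 24 hours for an SAE. Telephone visits may make the site aware sooner, but the 9.4.1 instruction is unchanged. Under Protocol 9.4.1 the diary holds the glucose value, symptoms and treatment; no field for seriousness or outcome is described.

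5. **Size.** Inputs: 42 randomized, about 36 completers, 12% dropout (Protocol 10.1, SAP 5.2).
   - Expected withdrawals for any cause: 0.12 × 42 = 5.04, about 5 (42 − 36 = 6 from the rounded targets).
   - One withdrawal moved into or out of the AE category: 1/42 = 0.0238, or 2.4 percentage points. If only the 36 completers received a given treatment, 1/36 = 2.8 points.
   - Serious nonsevere lows: the documents give no rate. Assumed range is 0 to 1 in the study.

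**The case against.** The strongest reply is that 9.4.1 is a routing instruction worded as a recommendation, not a redefinition of an AE. Appendix 1 and the duty to assess every AE for seriousness remain in force. This stands. A reader might infer that a serious nonsevere low cannot be reported as an SAE at all; the documents do not support that, because the general definitions point the other way. What they contain is an unresolved conflict.

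A reader might also infer that an injury during a self-treated low is lost. That does not follow. The instruction covers the hypoglycemic episode, not its consequences; an injury is an untoward occurrence in its own right and is reportable, as an SAE if it meets 9.2.1.

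Nor do nonsevere lows disappear from the trial. They are compared between treatments at both glucose thresholds (SAP Table ITSM.6.4), documented hypoglycemia is a secondary endpoint, and CGM episodes and time below range are analyzed (SAP 6.13). Withdrawals are summarized and every primary reason is listed (SAP 6.5). These analyses would reveal an excess of lows on either insulin better than a discontinuation table would.

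Two further backstops are weaker. Protocol 9.2 asks investigators to alert the sponsor to anything out of the ordinary, but sets no 24-hour limit there. The term search in SAP 6.10.4.1 looks only among reported AEs and summarizes those also reported as SAEs, so it cannot recover an event that was never entered.

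Finally, the eCRF completion instructions are not among the documents and may hold an exception. That is possible, but the protocol and SAP should not depend on it.

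**Conclusion.** The point holds as a conflict between passages that should be reconciled. Two kinds of event are exposed: a conscious patient hospitalized for the low alone (or meeting another 9.2.1 criterion without reaching Level 3), and a stop of IP because of nonsevere lows. A site that follows the hypoglycemia section as written would leave the first out of SAE reporting and the second out of the AE-discontinuation counts.

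The numerical effect is small. The range of 0 to 1 serious nonsevere lows is an assumption. The roughly 5 expected withdrawals are for all causes, and nothing in the documents says that any would be due to nonsevere hypoglycemia; the 2.4-point shift is therefore the effect of one hypothetical patient. No efficacy result, power or alpha is affected. The change is still worth making, because a stated rule, followed faithfully, can misroute a serious event.

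**What to change.** Add one sentence to Protocol 9.4.1 and the same to SAP 6.10.4.1: nonsevere hypoglycemia is not reported as an AE unless the episode meets a seriousness criterion in Protocol 9.2.1 or is the reason for stopping IP or leaving the study. In those cases it is entered on the AE page, and on the SAE page if serious, in addition to the hypoglycemia eCRF, and is counted in the SAE and AE-discontinuation summaries. Align the eCRF completion guidance.

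The cost is the text change and a few more AE pages. Routine lows stay where they are, and no dose, treatment or stopping rule changes.
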